Schedule of treatment and specimen collection:	
All patients will be scheduled to take deferiprone daily, 2 times a day, for up to 18 months.
 
Safety and efficacy assessments will be conducted at the following time points:
 
 • Hematology: Weekly up to Visit 4 (End of Study) or early termination • Blood chemistry: Visits 1, 2, 3, and 4 or early termination • ECG: Visits 1 and 4 or early termination • BAD: Visits 1, 2, 3, and 4 or early termination • PGI-I: Visits 2, 3, and 4 or early termination * 
* The PGI-I will be conducted at Visit 1 as well, but its data on that day will be applicable only to the initial study (for which this is the last visit), not to the extension study.
	
Statistical methods:	
Safety Analysis
 
The incidences of AEs and SAEs reported during deferiprone therapy for all patients, from the start of TIRCON2012V1 to the completion of TIRCON2012V1-EXT, will be tabulated. Similar tables will be produced for the severity of AEs and for their relationship to the study medication. Time to onset and duration of all AEs with an incidence of >5%, and of any AEs of special interest (e.g., worsening of dystonia), will be summarized with descriptive statistics.
 
The percentage of discontinuations due to AEs will be calculated, and the AEs leading to discontinuation will be summarized in a frequency table by preferred term.
 
Laboratory data (hematology and blood chemistry) will be summarized using descriptive statistics for continuous variables and frequency tables for discrete variables. The incidences of out-of-range data will be tabulated, and the changes from baseline to the end of study will be examined using shift tables.
 
Efficacy Analysis
 
For the efficacy measures of BAD (total score and by body region) and PGI-I, the change from baseline to each of the measurement time points will be determined and summarized using descriptive statistics. A paired t-test will be used to assess the statistical significance of the changes in these efficacy outcomes from baseline to Visit 4. For the BAD total score and for PGI-I, the proportions of patients determined to be responders at Visit 4 will be calculated and presented along with 95% confidence intervals.
	

Name of Sponsor: ApoPharma Inc.	Individual Study Table Referring to Part of the Dossier Volume: Page:	(For National Authority Use Only)
Name of Finished Product: Deferiprone		

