Patients who have experienced the same AE multiple times will be counted only once for the corresponding preferred term. Similarly, if a patient experiences multiple AEs within the same SOC, that patient will be counted only once for that SOC. AEs will be tabulated by presenting SOCs alphabetically and, within each SOC, presenting the preferred terms in decreasing order of the total number of patients who experienced each type of AE. In summaries presenting the incidence of AEs by intensity, seriousness, and relation to study medication, a patient with multiple events coded to a given preferred term or SOC will be counted only once for that preferred term or SOC according to the most severe event, the most serious event, or the event with the closest relationship to study medication.

Listings of SAEs, of withdrawals due to AEs, and of deaths will be provided separately and described in patient narratives.

ECG:

Clinically significant ECG abnormalities will be reported. The number and percentage of patients with normal and abnormal ECG results will be provided.

Vital Signs

Descriptive statistics (mean, median, standard deviation, minimum and maximum) will be presented for temperature, heart rate, respiratory rate, systolic blood pressure, diastolic blood pressure, weight, and height, at baseline and each relevant visit. Data will also be presented graphically for examination of possible trends.

Biochemistry and Hematology:

Descriptive statistics for each clinical laboratory test will be presented for each scheduled visit. According to the laboratory normal ranges, laboratory test results will be categorized as low (< lower normal limit), normal (within normal range), and high (> upper normal limit). Shift tables comparing the distributions of these 3 categories at baseline versus end of study will be presented. Continuous data will also be presented graphically for examination of possible trends.

Clinically significant laboratory values will be reported in the AE analysis.

Concomitant Medications

Medications will be coded using the WHO Drug dictionary. Medications taken during the course of the trial (on or after the first study drug dose and before or on the study termination date) will be considered as concomitant medications. Medications started after the study termination date will not be reported in tables, but will be presented in patient data listings. Concomitant medications used to treat adverse events will be differentiated from others.

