4.4.2 Laboratory Data

Descriptive statistics for each clinical laboratory test will be presented for each visit as defined above for hematology and for blood biochemistry. For each test, if multiple measurements are taken on the same scheduled visit for a subject, average value will be used for this subject at that visit. According to the laboratory normal ranges, laboratory test results will be categorized as low (< lower normal limit), normal (within normal range), and high (> upper normal limit). Shift tables comparing the distributions of these three categories at baseline versus end of study for parameters of interest will be presented.

Continuous data will also be presented graphically for examination of possible trends.

Clinically significant laboratory values will be reported in the adverse event analysis.

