14.3.2 Hematology and Biochemistry and Urinalysis	
Table 14.3.2.1.1	Hematology at each follow-up visit – safety population
Table 14.3.2.1.2	Hematology analysis: change in value at the end of study (Visit 4) – safety population
Table 14.3.2.1.3	Shift table comparing three laboratory value categories at baseline and end of study: Hematology – safety population
Table 14.3.2.2.1	Blood biochemistry at each follow-up visit – safety population
Table 14.3.2.2.2	Blood biochemistry analysis: change in value at the end of study (Visit 4) – safety population
Table 14.3.2.2.3	Shift table comparing three laboratory value categories at baseline and end of study: Blood biochemistry – safety population

Table 14.3.2.3.1 Proportions of abnormal urinalysis results in each visit – safety population

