	Month 24	xx xx.xx (xx.x) xx.x (xx.x, xx.x)

	Month 30	XX XX.XX (XX.X) XX.X (XX.X, XX.X)
	Month 36	XX XX.XX (XX.X) XX.X (XX.X, XX.X)
Repeat for other biochemistry parameters

Table 14.3.2.2.2 Blood biochemistry analysis: change in value at the end of study (Visit 4) – safety population

	Visit	n Mean (SD)	Change from Baseline n Mean (SD)	p-value [§]
Seum Ferritin (ug/L)	Baseline	xx xx.xx (xx.x)		
	Visit 4	xx xx.xx (xx.x)	xx xx.xx (xx.x)	0.xxxx
Repeat for other biochemistry parameters

§ p-value from paired t-test

Table 14.3.2.2.3 Shift table comparing three laboratory value categories at baseline and end of study: Blood biochemistry – safety population

Laboratory Test	Treatment	Baseline	End of study			Total
			Low	Normal	High	
Seum Ferritin	DFP	Low	xx	xx	xx	xx
		Normal	xx	xx	xx	xx
		High	xx	xx	xx	xx
		Total	xx	xx	xx	xx
Repeat for other tests of interest						

Table 14.3.2.3.1 Proportions of abnormal urinalysis results in each visit – safety population

Test	Visit	DFP (N=xx)
Abnormal Urinalysis n Abnormal (n (%))	Baseline	xx xx (xx)
	Month 1.5	xx xx (xx)
	Month 3	xx xx (xx)
	Month 6	xx xx (xx)
	Month 12	xx xx (xx)
	Month 18	xx xx (xx)
	Month 24	xx xx (xx)
	Month 30	xx xx (xx)
	Month 36	xx xx (xx)

Table 14.3.3.1 Summary of vital signs at each visit – safety population

Test	Visit	DFP (N=xx)
Resting Heart Rate n Mean (SD) Median (Min, Max)	Baseline	xx xx.xx (xx.x) xx.x (xx.x, xx.x)
	Month 1.5	xx xx.xx (xx.x) xx.x (xx.x, xx.x)
	Month 3	xx xx.xx (xx.x) xx.x (xx.x, xx.x)
	Month 6	xx xx.xx (xx.x) xx.x (xx.x, xx.x)
	Month 12	xx xx.xx (xx.x) xx.x (xx.x, xx.x)
	Month 18	xx xx.xx (xx.x) xx.x (xx.x, xx.x)
	Month 24	xx xx.xx (xx.x) xx.x (xx.x, xx.x)

	Month 30	xx xx.xx (xx.x) xx.x (xx.x, xx.x)
	Month 36	xx xx.xx (xx.x) xx.x (xx.x, xx.x)
Repeat for respiratory rate, systolic blood pressure, diastolic blood pressure

Table 14.3.3.2 Summary of weight at each visit – safety population

Test	Visit	DFP (N=xx)
Weight n Mean (SD) Median (Min, Max)	Baseline	xx xx.xx (xx.x) xx.x (xx.x, xx.x)
	Month 1.5	xx xx.xx (xx.x) xx.x (xx.x, xx.x)
	Month 3	xx xx.xx (xx.x) xx.x (xx.x, xx.x)
	Month 6	xx xx.xx (xx.x) xx.x (xx.x, xx.x)
	Month 12	xx xx.xx (xx.x) xx.x (xx.x, xx.x)
	Month 18	xx xx.xx (xx.x) xx.x (xx.x, xx.x)
	Month 24	xx xx.xx (xx.x) xx.x (xx.x, xx.x)

	Month 30	xx xx.xx (xx.x) xx.x (xx.x, xx.x)
	Month 36	xx xx.xx (xx.x) xx.x (xx.x, xx.x)

Table 14.3.3.3 Summary of height at each visit – safety population

Test	Visit	DFP (N=xx)

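### The SAP has no table for the out-of-range laboratory incidences promised in the protocol synopsis, and it limits the shift tables to unnamed parameters

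*SAP*

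**What the plan says.** The protocol synopsis, under statistical methods, covers hematology and blood chemistry together: "The incidences of out-of-range data will be tabulated, and the changes from baseline to the end of study will be examined using shift tables". Protocol 9.4.1.4 classifies each result as low, normal or high against the laboratory range and continues: "Shift tables comparing the distributions of these 3 categories at baseline versus end of study will be presented". Neither place restricts the tests. Section 9.4.1.4 does not repeat the incidence table.

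SAP 4.4.2 keeps the three categories for all laboratory results but uses them in one way only: "Shift tables comparing the distributions of these three categories at baseline versus end of study for parameters of interest will be presented". The parameters are listed nowhere. The shift-table shells in SAP section 7 show hemoglobin and serum ferritin and then say "Repeat for other tests of interest".

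For hematology and chemistry, the SAP table list has descriptive statistics by visit, change at Visit 4, and the shift table (for chemistry, "Shift table comparing three laboratory value categories at baseline and end of study: Blood biochemistry – safety population"). Urinalysis has a by-visit table of abnormal results: "Proportions of abnormal urinalysis results in each visit – safety population". SAP 4.4.2 also says: "Clinically significant laboratory values will be reported in the adverse event analysis".

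**The concern.** Hematology and blood chemistry are named primary endpoints (protocol 9.1.1; SAP 4.4). Urinalysis is not, yet it gets abnormal proportions at every visit and they do not. Apart from the shift tables, the summary tables for the two endpoints are built on means, medians and ranges. A minimum or maximum shows that an extreme value occurred, but not how many patients were out of range. SAP 4.4.2 also averages multiple measurements within a visit, which damps short excursions.

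The remaining categorical route for a value that is not in a shift table is the adverse event analysis. It depends on the investigator marking the value as clinically significant, in an open-label study. The synopsis table would have supplied a count that does not depend on that judgment. This matters for a product whose common reactions, according to protocol 1.3, include raised alanine aminotransferase.

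The unnamed parameter set is a second weakness. The SAP is dated April 2018 and reports completion counts from the initial study. For patients continuing on deferiprone, the safety period begins with that study, so part of their laboratory data already existed when the wording was written.

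**Working it through.** The documents give no figure to reproduce, so the check is a comparison of the texts followed by a count of visits.

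**Comparison**

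| Item | Protocol | SAP |
|---|---|---|
| Incidence of out-of-range hematology and chemistry values | Promised in the synopsis; not repeated in 9.4.1.4 | Absent from 4.4.2, the table list and the shells |
| Shift table, time points | Baseline to end of study (synopsis and 9.4.1.4) | Same |
| Shift table, tests | No restriction | Parameters of interest, not listed |
| By-visit abnormal proportions | Not specified | Urinalysis and ECG only |

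Two things changed between the documents: the incidence table disappeared and the set of tests was narrowed. The end-of-study time point did not change.

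**What happens to one abnormal value**

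- Marked clinically significant: it must be recorded as an adverse event (protocol 7.2.2) and enters the adverse event tables.
- Not clinically significant, on a selected test, still present at end of study: it is counted in the shift table.
- Not clinically significant, on a selected test, resolved by end of study: no categorical table.
- Not clinically significant, on an unselected test, resolved or not: no categorical table.

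The last two cases are the gap.

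**How much the shift table can see**

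Inputs: 44 patients continuing on deferiprone and 24 switched from placebo, 68 in all (SAP 3.2). Post-baseline chemistry months for continuers are 1.5, 3, 6, 12, 18, 24, 30 and 36, so 8 visits (SAP shell for Table 14.3.2.2.1). Switchers have Visits 2, 3 and 4, so 3 visits. Full attendance is assumed.

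- On-treatment chemistry visits: 44 × 8 + 24 × 3 = 352 + 72 = 424. End-of-study share: 68 / 424 = 16.0%.
- If the initial study took no chemistry at Months 1.5 and 3 (protocol 1.2 mentions only safety and efficacy assessments): 44 × 6 + 72 = 336, and 68 / 336 = 20.2%.
- Extension visits only: 68 × 3 = 204, and 68 / 204 = 33.3%.

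These shares apply even if all 18 chemistry tests in protocol 7.2.2 are selected. They count scheduled visits, not abnormalities, and follow from a format that uses one end value per patient.

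**The case against.** The incidence table rests on one synopsis sentence. Protocol 9.4 says the SAP will detail the specifications in that section, and 9.4.1.4 does not contain the table. This has some force, but the synopsis is part of the protocol, 9.4.1.4 does not contradict it, and the SAP does not mention the omission. Protocol 9.4 does allow changes in planned methods, provided they are documented in the study report.

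A reader might infer that the SAP introduced the end-of-study limit. It did not: the protocol states that limit twice.

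A reader might also infer that a patient whose abnormality resolved, or who left because of it, vanishes from the report. The documents do not support that:

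- End-of-study procedures, including chemistry, are done at an early-termination visit (protocol 7.2.2), and the SAP 4.4 windows classify safety data from patients who withdraw early. SAP 4.4.2 does not, however, say whether such a sample counts as end of study.
- Withdrawals due to adverse events are counted, listed and described in narratives (SAP 4.4.1).
- By-visit tables give minimum and maximum, SAP 16.3 plots the blood tests by patient, and SAP 16.2.8 lists all values.
- Confirmed neutropenia has its own reporting route (protocol 7.2.1.8), so the gap is smaller for neutrophil counts.

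Finally, in a single-arm study a count of any out-of-range value over many visits includes chance excursions and cannot by itself show a drug effect. That stands. It limits how the table is read, but does not justify leaving it out.

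**Conclusion.** The point holds in a bounded form. A tabulation promised in the protocol is missing from the SAP, and the shift tables are narrowed to a set that is not defined in advance. The result is that abnormalities judged not clinically significant enter no categorical table if they resolve by end of study or fall on an unselected test. For two primary safety endpoints, no objective count of patients with on-treatment abnormalities is planned.

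The number of abnormalities affected cannot be derived from the documents. It is tempting to read the 16% visit share as meaning that most on-treatment abnormalities are lost. That does not follow. The share depends on full attendance and on the assumed visit schedule, and going from visits to patients needs an assumption about persistence. If every abnormality on a selected test lasted to end of study, the shift table would miss none of the affected patients. Nor do the documents say that anyone chose parameters after seeing data; the wording only permits it.

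**What to change.** Add the table promised in the synopsis. For every hematology and chemistry test, give the number and percentage of patients with any on-treatment low value and with any high value, plus by-visit proportions in the format already planned for urinalysis. State that early-termination samples are included. Remove the parameters-of-interest qualifier from SAP 4.4.2 and the matching note in the shells, so that the shift tables cover all tests. If the sponsor prefers to keep the SAP's scope, it should list the shift-table parameters and document and justify the departure from the protocol.

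A shift from baseline to the worst on-treatment value would be a useful option, but neither document plans it, so it would be an addition and not a restoration.

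The cost is SAP wording and two or so extra standard tables from data already being collected. Any-visit counts should be labelled descriptive, because they will include chance excursions and grow with the number of samples per patient.

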4.4.3 Vital Signs, Weight and Height

Descriptive statistics will be presented for temperature, heart rate, respiratory rate, systolic blood pressure, diastolic blood pressure, weight, height, at baseline and each relevant visit. Data will also be presented graphically for examination of possible trends.

4.4.4 12-Lead ECG

Clinically significant ECG abnormalities will be reported. The number and percentage of patients with normal and abnormal ECG results will be provided.

Descriptive statistics will be presented for 12-lead ECG parameters at each relevant visit.

4.4.5 Treatment Compliance

Patients will be instructed on how to take the study medication. Compliance will be evaluated by calculating the volume of medication dispensed and the amount of unused drug supply remaining in the bottle. The compliance to the study medication at each visit will be summarized descriptively in a table.

4.4.6 Concomitant Medications

Medications will be coded using the World Health Organization (WHO) Drug Dictionary. Medications taken during the course of the trial (on or after the first study drug dose and before or on the study termination date) will be considered as concomitant medications. Medications started after the study termination date will not be reported in tables, but will be presented in patient data listings. Concomitant medications used to treat adverse events will be differentiated from others.

Concomitant medications will be summarized according to the preferred terms only. To count the number of patients who took a medication, a patient taking the same medication multiple times will only be counted once for that medication. Medications will be tabulated in decreasing order of the total number of patients who took each medication. In addition, the total number of patients to ever take any concomitant medications will be presented.

Concomitant medications will be presented based on the Safety population.

5 Listing of Tables and Figures

The listing of tables and figures shows the summary tables and figures that will be produced based on the statistical analysis detailed in this document. Summary tables and figures are numbered following ICH structure but the final numberings for tables and/or figures in the clinical study report can be changed if more tables and/or figures are added.

Tables Listing:

14.1 Disposition, Demographics and Baseline Data

Table 14.1.1	Number of patients in different populations
Table 14.1.2	Subject disposition – ITT population
Table 14.1.3	Subject exposure to study medication – ITT population
Table 14.1.4	Number of patients enrolled by study site – ITT population
Table 14.1.5	Summary of the reasons for not completing the study – ITT population
Table 14.1.6	Summary of demographics data at baseline of initial study – ITT population
Table 14.1.6a	Summary of demographics data at baseline of initial study – PP population
Table 14.1.7	Summary of baseline characteristics at the initial study – ITT population
Table 14.1.7a	Summary of baseline characteristics at the initial study – PP population

14.2 Efficacy Analyses

14.2.1 Analysis for All Patients on DFP

Table 14.2.1.1	BAD score at each follow-up visit by treatment group in initial study – ITT population
Table 14.2.1.1a	BAD score at each follow-up visit by treatment group in initial study – PP population
Table 14.2.1.2	BAD score at each follow-up visit for all patients on DFP – ITT population
Table 14.2.1.2a	BAD score at each follow-up visit for all patients on DFP – PP population
Table 14.2.1.3	Change in BAD score at each follow-up visit by treatment group in initial study – ITT population
Table 14.2.1.3a	Change in BAD score at each follow-up visit by treatment group in initial study – PP population
Table 14.2.1.4	Change in BAD score from baseline at each follow-up visit for all patients on DFP – ITT population
Table 14.2.1.4a	Change in BAD score from baseline at each follow-up visit for all patients on DFP – PP population
Table 14.2.1.5	BAD score per body region at each follow-up visit by treatment

	group in initial study – ITT population
Table 14.2.1.6	BAD score per body region at each follow-up visit for all patients on DFP – ITT population
Table 14.2.1.7	Change in BAD score per body region from baseline at each follow-up visit by treatment group in initial study – ITT population
Table 14.2.1.8	Change in BAD score per body region from baseline at each follow-up visit for all patients on DFP – ITT population
Table 14.2.1.9	Proportions of responders in BAD total score at each follow-up visit by treatment group in initial study – ITT population
Table 14.2.1.9a	Proportions of responders in BAD total score at each follow-up visit by treatment group in initial study – PP population
Table 14.2.1.10	Proportions of responders in BAD total score at each follow-up visit for all patients on DFP – ITT population
Table 14.2.1.10a	Proportions of responders in BAD total score at each follow-up visit for all patients on DFP – PP population
Table 14.2.1.11	PGI-I score at each follow-up visit by treatment group in initial study – ITT population
Table 14.2.1.11a	PGI-I score at each follow-up visit by treatment group in initial study – PP population
Table 14.2.1.12	PGI-I score at each follow-up visit for all patients on DFP – ITT population
Table 14.2.1.12a	PGI-I score at each follow-up visit for all patients on DFP – PP population
Table 14.2.1.13	Proportions of responders in PGI-I at each follow-up visit by treatment group in initial study – ITT population
Table 14.2.1.13a	Proportions of responders in PGI-I at each follow-up visit by treatment group in initial study – PP population
Table 14.2.1.14	Proportions of responders in PGI-I at each follow-up visit for all patients on DFP – ITT population
Table 14.2.1.14a	Proportions of responders in PGI-I at each follow-up visit for all patients on DFP – PP population
Table 14.2.1.15	Efficacy endpoints analysis for all patients on DFP: change in value at the end of study (Visit 4) – ITT population
Table 14.2.1.15a	Efficacy endpoints analysis for all patients on DFP: change in value at the end of study (Visit 4) – PP population
Table 14.2.1.15s	Efficacy endpoints analysis for all patients on DFP: change in value at the end of study (Visit 4) with imputed data – ITT population
Table 14.2.1.15.1	Efficacy endpoints analysis for all patients on DFP: change in value at the end of study (Visit 4) – ITT population and age at onset < 6 years
Table 14.2.1.15.2	Efficacy endpoints analysis for all patients on DFP: change in value at the end of study (Visit 4) – ITT population and age at onset ≥ 6 years
Table 14.2.1.15.3	Efficacy endpoints analysis for all patients on DFP: change in value at the end of study (Visit 4) – ITT population and DBS = Yes

Table 14.2.1.15.4	Efficacy endpoints analysis for all patients on DFP: change in value at the end of study (Visit 4) – ITT population and DBS = No
Table 14.2.1.15.5	Efficacy endpoints analysis for all patients on DFP: change in value at the end of study (Visit 4) – ITT population and Region = US
Table 14.2.1.15.6	Efficacy endpoints analysis for all patients on DFP: change in value at the end of study (Visit 4) – ITT population and Region = Europe
Table 14.2.1.15.7	Efficacy endpoints analysis for all patients on DFP: change in value at the end of study (Visit 4) – ITT population and Duration of disease > 5 years
Table 14.2.1.15.8	Efficacy endpoints analysis for all patients on DFP: change in value at the end of study (Visit 4) – ITT population and Duration of disease ≤ 5 years
Table 14.2.1.16	Efficacy endpoints analysis for all patients on DFP: proportions of responders in BAD total score and PGI-I at the end of study (Visit 4) – ITT population
Table 14.2.1.16a	Efficacy endpoints analysis for all patients on DFP: proportions of responders in BAD total score and PGI-I at the end of study (Visit 4) – PP population
Table 14.2.1.16s	Efficacy endpoints analysis for all patients on DFP: proportions of responders in BAD total score and PGI-I at the end of study (Visit 4) with imputed data – PP population
Table 14.2.1.17	Trend analysis by MMRM model on BAD total score and by body region for all patients – ITT population

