3.3 Analysis Populations

The following study populations will be used for analysis: Safety, Intent-to-Treat (ITT), and Per-Protocol (PP). The safety population will be used for the analysis of safety endpoints. The ITT population will represent the primary analysis population for the evaluation of efficacy endpoints, and the PP population will be the secondary efficacy analysis population.

Safety Population

The Safety population will include all patients who took at least one dose of study drug in the extension study.

ITT Population

The ITT population will include all enrolled patients who received at least one dose of study drug and have a baseline and at least one post-baseline efficacy assessment in the extension study.

PP Population

The PP population will include all enrolled patients who complete the extension study and have an efficacy assessment at the end of the study, have no major protocol violations, and have no change in DBS and baclofen pump settings or medications that could have an impact on dystonia. Prior to database lock, protocol deviations and medications that could have an impact on dystonia will be reviewed for their seriousness, and patients with major deviations will be excluded from the PP population.

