3.5 Missing Data Handling and Derivation Rules

For safety data analysis, no imputation will be performed on the missing data and analysis will be based on observed cases.

For efficacy endpoints, the continuous variables will be summarized and analyzed as recorded on the case report forms (CRFs). If statistically significant imbalances are detected in the incidence of changes in DBS settings and outcome impacting medication use as well as the frequency of PRN drug or rescue medication between the initial study and the extension study, a Mixed-Effect Model Repeated Measure (MMRM) model will be used as the analysis method to compare the change in score from baseline between the initial study and the extension study for patients who received placebo in initial study (TIRCON2012V1) and the analysis will be based on observed cases. If no significant imbalance was detected, the paired t-test will be used as the analysis method and the last observed data will be used.

For the efficacy analysis on all patients who received DFP during the initial and the extension study, the last observation will be used to calculate the change from baseline for patients terminated early. As a sensitivity analysis, for early termination due to worsening of disease conditions or inadequate efficacy of the drug, as indicated in the CRF, the “worst score” method will be used for data imputation. That is, for continuous variables such as BAD total score at a particular time point, the worst score of all patients will be used to impute the missing data at that time point. For categorical variable such as responder, the worst category (treatment failure) will be assigned. For missing data due to missed visit, the last observation will be used to fill the void.

For BAD total score, if one or several component scores cannot be measured, then the same component score from the last visit will be carried forward and if it is also missing, the score from the next visit will be carried backward to fill the missing component score(s) before the total score is calculated.

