4.3.2 Exploratory Analyses/Sensitivity Analysis

In order to explore potential differences in the change in BAD from baseline to Visit 4 and PGI-I at Visit 4 across population subgroups, subgroup analyses will be performed for the ITT population on the following factors assessed at the baseline of the initial study: Age at onset of motor symptoms (<6 years vs. ≥ 6 years), DBS (Deep Brain Stimulation, Yes vs. No), Region (US vs. Europe), and Duration of disease (>5 years vs. ≤ 5 years).

Besides analysis for the ITT population, the efficacy analyses will also be repeated for outcomes defined based on BAD total score and PGI-I for the PP population as sensitivity analyses.

As a sensitivity analysis, the statistical analysis on the change in the BAD total score from baseline to Visit 4 and PGI-I at Visit 4 will be repeated with the missing data being imputed as described in section 3.5 based on the ITT population.

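### SAP section 5 lists the imputed-data responder table (14.2.1.16s) on the per-protocol population, where the treatment-failure rule cannot change any patient; the rest of the SAP points to ITT

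*SAP*

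**What the plan says.** - **Table listing.** SAP section 5, under 14.2.1, gives three versions of the Visit 4 responder table for all patients on deferiprone: 14.2.1.16 on ITT, 14.2.1.16a on PP, and 14.2.1.16s, whose title ends "with imputed data – PP population".
- **PP definition.** SAP 3.3: "The PP population will include all enrolled patients who complete the extension study and have an efficacy assessment at the end of the study". It also excludes patients with major violations or with changes in DBS or pump settings or dystonia-relevant medication. Protocol 9.3.2 likewise requires completion and an end-of-study assessment.
- **Imputation rule.** In the main all-patients analysis, SAP 3.5 uses the last observation for patients who stopped early. Its sensitivity method replaces that value "for early termination due to worsening of disease conditions or inadequate efficacy of the drug, as indicated in the CRF". For responders: "For categorical variable such as responder, the worst category (treatment failure) will be assigned". A separate rule follows: "For missing data due to missed visit, the last observation will be used to fill the void".
- **Population for that sensitivity analysis.** SAP 4.3.2 repeats the analysis of BAD change and PGI-I at Visit 4 "with the missing data being imputed as described in section 3.5 based on the ITT population".
- **Companion table.** 14.2.1.15s is listed as "change in value at the end of study (Visit 4) with imputed data – ITT population".
- **Conventions.** SAP section 7 says that the end of a table's title states its analysis population, that suffix a marks PP tables and that suffix s marks sensitivity tables. Its shell introduces 14.2.1.16s as a variant of the ITT-titled 14.2.1.16 and names no PP restriction.

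**The concern.** A responder, under SAP section 4, is a patient who has not worsened: a BAD change of zero or less, or a PGI-I rating of no change or better. Under last observation, a patient who left because of worsening still counts as a responder if the last recorded score had not deteriorated. The treatment-failure rule exists to test how much that matters. The SAP allows for such departures, since the shell for Table 14.1.5 has a row for worsening or lack of efficacy.

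Table 14.2.1.16s is the only listed all-patients responder table that uses imputed data. If it is programmed from its title, the patients the rule is meant for are removed before the rule is applied. The result would carry a sensitivity-analysis label, would probably look much like 14.2.1.16a, and could be read as showing robustness to dropout that it has not tested.

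**Working it through.** The plan states no figure for this point, so the check is mainly one of logic.

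**1. Can the failure rule act on a PP patient?**

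- PP membership requires completion of the extension, an end-of-study efficacy assessment, no major violation, and no DBS, pump or dystonia-medication change (SAP 3.3).
- The failure rule requires early termination for worsening or inadequate efficacy (SAP 3.5).
- Completion and early termination exclude each other. Going through every combination of completed, assessed, major deviation, setting or medication change, and terminated for worsening, and dropping the impossible pair of completed and terminated, leaves one profile that qualifies for PP. None of the profiles that meet the failure trigger is in PP.

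Patients recoded to failure in 14.2.1.16s as listed: 0, whatever the data show.

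**2. Can any other filling act within PP?**

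Yes, to a small extent. PP asks for an efficacy assessment, not for both instruments. A completer with BAD but no PGI-I at Visit 4, or the reverse, could have the missing one carried forward. A missing BAD component could be filled from the previous or the next visit. The component rule in SAP 3.5 is not confined to the sensitivity analysis, so if it is applied in 14.2.1.16a too, it makes no difference between the two tables.

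**3. Which population do the other parts of the SAP indicate?**

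| Place in SAP | Indicates |
|---|---|
| Section 5, title of 14.2.1.16s | PP |
| Section 4.3.2, imputation sentence | ITT (responder proportions not named) |
| Section 5, title of 14.2.1.15s | ITT |
| Section 7, shell for 14.2.1.16s | Variant of an ITT table |
| Section 7, suffix rule | Suffix a for PP, so s alone does not mark PP |

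**4. What could the rule do on ITT? (illustration)**

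- Enrolled: 44 + 24 = 68 (SAP 3.2). ITT also requires a dose, a baseline and a post-baseline assessment, so N is at most 68.
- One last-observation responder recoded to failure shifts the proportion by 1/N. With N = 68, 1/68 = 1.47 percentage points; with a smaller N the shift is larger.
- A recoded patient who was already a non-responder shifts it by 0.
- Assume N = 68 and 34 responders by last observation, 34/68 = 50.0%. Neither that rate nor the counts recoded below are in the documents.

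| Responders recoded | Proportion on ITT | Shift (points) | Shift from this rule on PP |
|---|---|---|---|
| 2 | 32/68 = 47.1% | -2.9 | 0 |
| 4 | 30/68 = 44.1% | -5.9 | 0 |
| 7 | 27/68 = 39.7% | -10.3 | 0 |
| 10 | 24/68 = 35.3% | -14.7 | 0 |

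**The case against.** The strongest reply is that this is a labelling slip. One listing line says PP, while four other places indicate ITT, and a careful programmer would probably query it. SAP 4.3.2 also imports the method of section 3.5, which covers responders explicitly, so the rule itself is not missing. The stakes are limited as well: this is a sensitivity table for secondary endpoints in a single-arm, open-label safety extension; the all-patients responder result is a proportion with a confidence interval and no test; the main responder table is on ITT; and worst-score imputation is still examined on ITT for the BAD change and PGI-I scores in 14.2.1.15s.

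Most of this stands. PP is very likely not what was intended, and the point is an inconsistency within the SAP rather than a deliberate analysis choice. It still needs correcting, because SAP section 7 makes the title the place where the population is stated, section 5 says that the listed tables are the ones to be produced, and the sentence in 4.3.2 that could override the title does not name the responder proportions.

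A reader might infer more: that nothing at all would be imputed, that no PP patient can lack a Visit 4 value, and that 14.2.1.16s must equal 14.2.1.16a. The documents do not support this. PP requires only one efficacy assessment, so carry-forward of a single missing instrument remains possible.

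**Conclusion.** The point holds for the treatment-failure rule. As listed, Table 14.2.1.16s cannot show any effect of counting early terminations for worsening or inadequate efficacy as failures; the effect of that rule is exactly zero by construction. This rests only on the definitions in SAP 3.3 and 3.5.

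What is lost on ITT cannot be sized from the documents. About 1.5 points per recoded responder is an illustration at N = 68, not an upper bound: a smaller ITT makes each shift larger, and a patient who is already a non-responder contributes none. The early termination visit collects both BAD and PGI-I, so some patients who leave for worsening may already be non-responders by last observation. The number leaving for this reason is not stated.

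The correction should be made, but it does not touch the primary safety objective or the main efficacy tables.

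**What to change.** 1. In the SAP section 5 listing, change the population in the title of Table 14.2.1.16s from PP to ITT. The shell in section 7 needs no change.
2. In the imputation sentence of SAP 4.3.2, name the BAD and PGI-I responder proportions at Visit 4 alongside the BAD change and the PGI-I score.

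The cost is one table title and one sentence. No new data are needed, and the imputation rule is already written in section 3.5. If the table has already been produced from the listing, it has to be rerun on ITT.
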